4.4 End of Study Definition

All patients who participate in this study and complete Visit 9 (End of Study/Early Termination) visit are considered to have completed the study (Table 1).

The end of the study is defined as the date of the last visit of the last patient in the study.

5 Study Population

Prospective approval of protocol deviations to eligibility criteria, also known as protocol waivers or exemptions, are not permitted.

The patients possibly eligible will be identified as the follows:

1. Patients identified during their routine endoscopy:
 - Patients must have erosive esophagitis identified during the routine endoscopy, before being considered for study screening (prior to signing the ICF).
 - This routine endoscopy will also serve as the index endoscopy in the study and the report should contain the endoscopy findings using the Los Angeles (LA) classification.
 - This routine endoscopy must be obtained within 7 working days of planned randomization, please refer to [Inclusion criterion #4](#).
2. Patients invited for screening upper endoscopy based on their past medical history (both criteria must be met):
 - a) LA grade C or D disease within the past 5 years before screening, demonstrated with endoscopy (endoscopy report issued by a gastroenterologist/endoscopist is accepted)
 - b) In the Investigator's judgement the patient presents clear symptom relapse: patient may be treated with PPI, discontinued PPI treatment (patient's decision) or is being treatment naïve.

For patients invited for screening upper endoscopy, the ICF will be signed prior to the endoscopy. The screening procedures must start with endoscopy and in case the patient doesn't show LA grade C or D erosions, the rest of the screening procedures must not be conducted. This screening endoscopy must be obtained within 7 working days of planned randomization.

The index/screening endoscopy video/digital image will be anonymized and saved for central storage. Imaging data must meet quality standards for adequate LA grading and must be accompanied by a report and videos/digital images to allow retrospective analysis of the endoscopy findings.

Investigators must keep a record of all screened patients even if they were not subsequently randomized in the study. This information is necessary to verify that patients were selected

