5.1 Inclusion Criteria

For inclusion in the study, patients must fulfill the following criteria:

1. Written informed consent must be obtained before any study related assessment is performed.
2. Male or female patient aged 18-75 years inclusive at the time of obtaining the informed consent.
3. Body mass index (BMI) ≥ 18 and ≤ 40 kg/m² at screening
4. Gastroesophageal reflux disease with endoscopically confirmed erosive esophagitis:
 - LA grade C or D ≤ 7 working days before randomization (with or without historical PPI treatment)
or
 - LA grade A or B ≤ 7 working days before randomization
and
 - history of treatment with standard healing course of PPI* for minimum of 8 weeks prior to screening and ≤ 7 working days of non-treatment during this period**.
and
 - at least partial symptom response during the minimum of 8 weeks of PPI treatment.

Note: Partial symptom response is defined as a clear symptom improvement (heartburn or regurgitation) after start of the PPI treatment course. To qualify, the patient's response must be YES to the Investigator's standardized question to the patient: Did you feel a clear symptom improvement in heartburn or regurgitation after you started the PPI treatment course?

* All PPIs EXCEPT lansoprazole

** Non-treatment days are counted from the last day of standard healing course of PPI therapy until endoscopy used for eligibility assessment demonstrating erosive esophagitis due to GERD.”

5. Willing and able to comply with all aspects of the protocol (including PK sampling, capsule swallowing, diary completion, etc.)

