4.10.3 Secondary Efficacy Variables

Analyses of the secondary efficacy endpoints will be performed for the FAS and the PP as defined in Section 4.5.

QOLRAD scores and mRESQ-eD means or proportions will be estimated using a Generalized Linear Mixed Model (GLMM) approach using information of each week for each subject, on observed data, assuming missing at random.

The models will be implemented using all available timepoints (as categorical), the X842 dose level or lansoprazole as covariate and the related interaction, center and erosive esophagitis due to GERD (LA grade C or D / LA grade A or B).

Toeplitz covariance matrix will be assumed. In case of convergence failure, the following matrices will be tested until convergence is reached: 1. Compound Symmetry, 2. Autoregressive 1 (AR-1).

Mean and standard error estimated from the model will be provided in the outputs. Median, Q1, Q3, Min and Max will be reported as observed data.

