The domain severity or frequency on a given day, morning or evening will be derived as the highest severity or frequency of the items that form the domain. If some items are missing, the highest value will be chosen amongst available items.

Heartburn domain:

- Morning score: the highest severity score between item 1 and item 2 of the morning assessment (min-max 0-5).
- Evening score: the highest severity score between item 1 and item 2 of the evening assessment (min-max 0-5)
- Daily score: the highest severity score between daily assessments of item 1 and item 2 (min-max 0-5)

Regurgitation domain scores are constructed in the same way as Heartburn domain using the items that form the domains.

Weekly means of the daily scores, of the morning scores and of the evening scores will then be calculated and presented by week for each domain or item. A minimum of 4 days during a week with severity or frequency of symptoms recorded is required to calculate weekly means for all the 3 domains.

Heartburn free:

Heartburn-free in a 24-hour day is defined as a daily score of 0 for the heartburn domain, and the number of heartburn-free days over a week will be calculated. The percentage of heartburn-free days for a patient over a week will be calculated as:

% heartburn-free days = number of days with daily score =0 / number of days the severity of symptom is recorded x 100.

A minimum of 4 days during a week with severity of symptoms recorded is required, otherwise, the percentage will be set as missing for that week.

The percentage of heartburn-free in the morning and heartburn-free in the evening will also be calculated for morning and evening records respectively.

Heartburn with at most mild symptoms:

Heartburn with at most mild symptoms (either no symptoms, very mild symptoms or mild symptoms) in a 24-hour day is defined as all the items in the domain that have a daily score of maximum 2, and percentage of heartburn- at most mild symptoms days for a patient over a week will be calculated as:

% heartburn-at most mild symptoms days = number of days where all items have daily score ≤ 2 / number of days the severity of symptom is recorded x 100.

A minimum of 4 days during a week with frequency of symptoms recorded is required, otherwise, the percentage will be set as missing for that week.

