4.10.3.3 Heartburn assessed by investigator

At each visit, Investigator will assess the severity of patients' heartburn, regurgitation and dysphagia in the 7 days prior to the visit. The assessment will include both the severity grade and the frequency of symptoms.

The potential frequency is defined as one of these grades: All of the time, Most of the time, Quite a lot of the time, Some of the time, A little of the time, Hardly any of the time and None of the time. Symptoms are scored as either none, mild, moderate or severe.

The following summaries will be provided by study treatment group and visit:

- A summary of investigator assessment of symptoms (severity and frequency of heartburn, regurgitation and dysphagia) at Weeks 1-8 (Visits 2-9) (FAS/PP)
- A bar chart of investigator assessment of heartburn (severity and frequency) at baseline and from 1 to 8 weeks of treatment (FAS/PP)
- A bar chart of investigator assessment of regurgitation (severity and frequency) at baseline and from 1 to 8 weeks of treatment (FAS/PP)
- A bar chart of investigator assessment of dysphagia (severity and frequency) at baseline and from 1 to 8 weeks of treatment (FAS/PP)

A listing of investigator assessment of symptom at Weeks 1-8 (Visits 2-9) will be provided:

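### The model for the two heartburn diary endpoints omits the entry heartburn rating already scheduled for every patient; adding it is a nearly free gain in precision, and a split by that rating would make the dose pattern readable.

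*SAP*

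**What the plan says.** **Model.** SAP 4.10.3 fits a generalized linear mixed model with time as a category plus "the X842 dose level or lansoprazole as covariate and the related interaction, center and erosive esophagitis due to GERD (LA grade C or D / LA" (the list ends with the A/B level). No symptom measure from before treatment is included. Section 4.5.1.1 of the SAP amendment changes covariates for the primary dose-response model only.

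**Endpoints.** Under SAP 4.10.3.2, "Heartburn-free in a 24-hour day is defined as a daily score of 0 for the heartburn domain", and the weekly figure is "heartburn-free days = number of days with daily score =0 / number of days the severity of symptom is recorded x 100". The at-most-mild endpoint is built the same way with a cut-off of 2. Both are levels during treatment. QOLRAD, by contrast, is also summarised as change from baseline (4.10.3.1).

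**Entry.** Protocol 5.1, criterion 4, admits "LA grade C or D ≤ 7 working days before randomization (with or without historical PPI treatment"), or grade A/B with "at least partial symptom response during the minimum of 8 weeks of PPI treatment". Its note reads: "Partial symptom response is defined as a clear symptom improvement (heartburn or regurgitation) after start of the PPI treatment course". Current symptoms are required on one route only, that of patients with earlier C/D disease invited for endoscopy (Protocol Section 5): "In the Investigator's judgement the patient presents clear symptom relapse".

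**Data at hand.** SAP 4.10.3.3 states: "At each visit, Investigator will assess the severity of patients' heartburn, regurgitation and dysphagia in the 7 days prior to the visit". Protocol Table 1 schedules this at Visits 1 and 2, and Protocol Section 8 places it before dosing in its preferred order. The SAP summarises and charts it by arm but does not use it in the diary model. The diary itself is handed out at Visit 2, so a diary baseline is at most the pre-dose entries of Day 0, where these exist.

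**Subgroups.** The diary endpoints are split by LA grade, age and sex (SAP 4.10.1.6), with center added in amendment 4.5.5.2. No split uses entry symptoms.

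**The concern.** The secondary symptom objective is to describe the symptom pattern under each dose. Criterion 4 selects on endoscopy and, for A/B patients, on past improvement under PPI. It does not select on present heartburn, and improvement in regurgitation alone is enough. An unknown share of patients may therefore start with little or no heartburn and have little room to improve on an endpoint that counts heartburn-free days.

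Two separate things follow:

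- **Dilution.** If those patients score high in every arm, the difference between doses is smaller in the whole group than in patients who have the symptom. A flat pattern could then mean equal effect or a ceiling, and the planned tables do not separate the two.
- **Noise.** With about 48 patients per arm, chance imbalance in entry heartburn moves the arm means, and the model does nothing to remove it.

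**Working it through.** **Inputs from the documents.** There are 48 patients per arm (Protocol 1.1 and 6.3.1; 5 × 48 = 240). The sample-size sections are blacked out. No symptom-free share, diary effect or SD is given, so there is no plan figure to reproduce. Everything below rests on assumptions.

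**Assumed set A.** Patients with heartburn at entry average 45% and 65% heartburn-free days in two arms (20 points apart), SD 35. Symptom-free entrants average 97%, SD 6, in both arms. Their share f runs from 10% to 50%.

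**Step 1, dilution.** Let δ be the arm difference among symptom-free entrants. The overall difference is (1 − f) × 20 + f × δ.

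- With δ = 0: 18, 16, 14, 12 and 10 points at f = 10, 20, 30, 40 and 50%.
- If these patients lose control in the lower-dose arm (assumed 80% against 97%, δ = 17), at f = 30%: 0.7 × 20 + 0.3 × 17 = 14 + 5.1 = 19.1 points.
- With δ = 20 there is no dilution.

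**Step 2, chance imbalance.** The SD of the between-arm difference in symptom-free share is √(2f(1 − f)/48). The gap between the two kinds of patient is 97 − (45 + 65)/2 = 42 points. At f = 30%: √(0.42/48) = 0.0935, and 0.0935 × 42 = 3.9 points. Across f = 10% to 50% the range is 2.6 to 4.3 points.

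**Step 3, what a covariate does.** In 2,000 simulated trials per share, with two arms of 48 and δ = 0, the mean difference (SE) was:

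| f | Unadjusted | Entry symptoms as main effect | Symptomatic patients only |
|---|---|---|---|
| 10% | 18.1 (7.3) | 18.2 (6.9) | 20.0 (7.6) |
| 20% | 16.0 (7.4) | 16.2 (6.6) | 20.1 (8.0) |
| 30% | 13.9 (7.3) | 14.0 (6.2) | 19.9 (8.8) |
| 40% | 12.1 (7.2) | 12.0 (5.9) | 20.0 (9.5) |
| 50% | 9.9 (6.8) | 10.0 (5.3) | 20.0 (10.4) |

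The covariate leaves the difference where it was and shrinks its variance: 1 − (6.9/7.3)² = 11% at f = 10%, 1 − (6.2/7.3)² = 28% at 30%, and 1 − (5.3/6.8)² = 39% at 50%. Only the separate estimate recovers the 20 points, with a larger SE.

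**Assumed set B.** Symptomatic patients average 55% against 70% (15 points), SD 35; symptom-free entrants average 95%, SD 10. At f = 20, 35 and 50% the difference is (1 − f) × 15 = 12.0, 9.8 and 7.5 points. With 95 − 62.5 = 32.5, entry status explains f(1 − f) × 32.5² / [f × 10² + (1 − f) × 35² + f(1 − f) × 32.5²] = 14, 22 and 28% of outcome variance.

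**Limits.** The simulated covariate is true symptom status. A four-grade investigator rating is a proxy, so the real gain should be smaller. The simulation uses one outcome per patient rather than eight weekly values, and has no center or LA term.

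**The case against.** The strongest reply is that little depends on this. The endpoints are secondary, the protocol analyses them descriptively (9.4.7), and no formal testing is planned (SAP 4.10.1.4). The Phase 3 dose is to rest on healing, safety and PK (Protocol 2.2). This stands and limits the weight of the point.

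Entry symptoms are also partly visible already, through the baseline charts of investigator-rated heartburn and the change in QOLRAD. Protocol 9.4.7 plans an exploratory change from baseline in the diary by healing status; what the SAP does with it is blacked out. This stands in part: a chart can show an imbalance but does not correct for it, and none of the visible analyses splits the two diary endpoints by entry heartburn.

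A reader might infer that symptom-free entrants will score close to 100% in every arm. The documents do not support that. Improvement on PPI is not absence of symptoms, and one recruitment route requires relapse. PPIs are barred from screening onward (Protocol 5.3 and 5.3.2). An A/B patient may be up to 7 working days off PPI at endoscopy, and endoscopy may precede randomization by up to 7 more. The lowest dose was chosen to be slightly less effective than the comparator (Protocol 2.3). Loss of control could therefore depend on dose, and the endpoint would register it.

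Finally, a new covariate or split now comes after unblinding (SAP amendment, Section 3). That is correct and governs how the result is labelled.

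**Conclusion.** The point holds as a low-cost improvement. The plan leaves out a baseline rating that it collects in every patient and that plausibly predicts both diary endpoints. Under the assumptions shown, using it would cut the variance of an arm difference by roughly 11% to 39%, less to the extent that the rating is an imperfect proxy.

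Dilution is possible, but its size is unknown. It ranges from none to about half of the effect, depending on the symptom-free share and on whether such patients relapse by dose after stopping PPI.

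A reader might also infer that the missing covariate is what flattens the dose pattern. It is not. Randomization balances entry symptoms in expectation, and a main effect leaves the expected difference in arm means unchanged (13.9 against 14.0 points at a 30% share). Dilution comes from who is enrolled and how the endpoint is defined; only estimates by entry status show it. Nothing here bears on the healing result.

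**What to change.** 1. In the model for the two heartburn diary endpoints, add investigator-rated 7-day heartburn severity at Visit 2, or at Visit 1 if Visit 2 is missing. Report this beside the planned model.
2. Tabulate both endpoints by treatment and by entry heartburn (none, any), with patient counts. Show both strata: patients rated none may be controlled by recent PPI, and a dose effect may appear in them as loss of control. A table limited to symptomatic patients would hide that.
3. State that the covariate addresses precision and chance imbalance, while the table addresses dilution. Label both exploratory, in line with the results hierarchy in section 4.3.3 of the SAP amendment.

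The cost is a short addition to the SAP, one covariate and one table per endpoint, from data already scheduled. The price is small strata: a 30% share gives about 0.3 × 48 = 14 patients per arm rated none, and in the simulation the symptomatic-only estimate had an SE of 8.8 against 7.3 for the whole group. The table should be read as description.

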4.10.3.1 QOLRAD

Reflux related impact will be assessed based on the patient reported outcome (PRO) QOLRAD. The heartburn version of the QOLRAD is a disease specific instrument and contains 25 questions addressing concerns associated with gastrointestinal symptoms. Each question is scored from 1 to 7, where a higher score represents a higher (“better”) health-related quality of life.

The QOLRAD will be completed pre-dose by patients at Visits 2 (Baseline), 3 (Week 1), 4 (Week 2), 5 (Week 4), and 9 (Week 8) (see Table 1 in section 6.1).

The questions are categorized into five domains: emotional distress (six questions), sleep disturbance (five questions), vitality (three questions), food/drink problems (six questions) and physical/social functioning (five questions).

- Emotional distress (questions 12, 14, 15, 17, 19, 22)
- Sleep disturbance (questions 8, 10, 11, 18, 21)
- Food/drink problems (questions 3, 5, 9, 13, 16, 20)
- Physical/social functioning (questions 2, 6, 23, 24, 25)
- Vitality (questions 1, 4, 7)

For the calculation of domain scores, in case of missing items, these missing items can be replaced under specific conditions (the half-scale method) as follows:

- If 50% or more of the questions in one dimension are completed, the mean value of the completed items should replace the missing responses.

- If less than 50% of the questions in one dimension are completed, the missing responses will not be replaced.

The score in each domain will be calculated as the mean of all items in that domain, only if all items are not missing after replacement.

To evaluate the reflux related impact pattern during the initial 4 weeks treatment and the subsequent additional 4 weeks (Weeks 5-8) open-label treatment with lansoprazole 30 mg QD, the following summaries will be provided by study treatment group and assessment day:

- A summary of QOLRAD domain scores and change from baseline (FAS/PP)
- A plot of QOLRAD domain scores at baseline and Week 1, Week 2, Week 4 and Week 8 (FAS/PP).

A listing of QOLRAD results will be provided. Original values and imputed values will be provided, together with domain scores.

4.10.3.2 mRESQ-eD

Reflux related symptoms will also be assessed based on the modified RESQ-eDiary. mRESQ-eD contains 8 items where 5 items assess severity (Did not have – Severe) and 3 items assess frequency (Never – Very often) of symptoms.

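### The covariance structures named for QOLRAD ignore its unequal visit spacing and assume one variance, so the standard errors of change from baseline may be biased

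*SAP*

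**What the plan says.** SAP 4.10.3 sets one repeated-measures model for both QOLRAD and the symptom diary: "The models will be implemented using all available timepoints (as categorical), the X842 dose level or lansoprazole as covariate and the related interaction", plus center and LA grade group. The covariance rule is "Toeplitz covariance matrix will be assumed". If that fails to converge, "the following matrices will be tested until convergence is reached: 1. Compound Symmetry, 2. Autoregressive 1 (AR-1"). The reported quantities are model-based: "Mean and standard error estimated from the model will be provided in the outputs". The readable text names no unstructured, unequal-variance or time-distance structure, and no sandwich SE.

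The two instruments run on different clocks. SAP 4.10.3.1 has QOLRAD completed at "Visits 2 (Baseline), 3 (Week 1), 4 (Week 2), 5 (Week 4), and 9 (Week 8"), so neighbouring visits are 1, 1, 2 and 4 weeks apart. The diary is summarised weekly over Weeks 1–8 (SAP 4.10.3.2), which is equal spacing. The QOLRAD endpoint in SAP 2 and 3.2.1.2 is change from baseline at 1, 2, 4 and 8 weeks, and 4.10.3.1 plans a table of scores and change.

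The SAP amendment follows the original SAP unless it says otherwise (its Section 1). Its readable text does not alter the covariance rule.

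**The concern.** Toeplitz and AR(1) work on visit order. They give the Week 0–1 pair and the Week 4–8 pair the same correlation, although the second gap is four times as long and spans the switch of all patients to open-label lansoprazole. Compound symmetry uses neither order nor time: it assumes that correlation does not decay at all. All three also force one variance on every visit. QOLRAD items are bounded at 1 and 7, with higher scores better, so variance could plausibly shrink as patients improve.

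The SE of a change depends directly on the correlation between the two visits. If that correlation is wrong, the stated precision of the change is wrong too, in either direction. With no sandwich SE planned, nothing corrects it. What is at stake is the precision reported for one secondary endpoint, including any 95% confidence intervals shown under SAP 4.2.

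**Working it through.** The plan gives no QOLRAD SD, correlation or SE, so there is no figure to reproduce. The check asks how far the model-based SE departs from the true SE under stated assumptions.

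**Inputs.** From the documents: visits at weeks 0, 1, 2, 4 and 8; the three structures; about 240 patients, 48 per arm. Assumed: true correlation r^|t−s| in real weeks with r = 0.7, 0.8 or 0.9, or constant 0.6; SD equal at all visits, or falling; baseline modelled as a visit; complete data.

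**Method.** For each true 5×5 matrix, find the closest matrix of the named structure (maximum expected normal log-likelihood). Then take the ratio of model SE to true SE. The number per arm cancels. For change from baseline to visit k with equal variances,

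ratio = √[(v − c_k) / (1 − r^t_k)],

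where v is the fitted variance, c_k the fitted covariance with baseline, and the true variance is 1.

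**Toeplitz, Week 1.**
- r = 0.7: v = 0.9992, c = 0.5314, so √(0.4678/0.300) = 1.25.
- r = 0.9: v = 0.9990, c = 0.8155, so √(0.1835/0.100) = 1.35.

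**Compound symmetry.** The fitted correlation is the mean over the ten visit pairs, whose gaps are 1, 1, 2, 2, 3, 4, 4, 6, 7 and 8 weeks.
- r = 0.7: mean 0.346. Week 1: √(0.654/0.300) = 1.48. Week 8: √(0.654/0.942) = 0.83.
- r = 0.9: mean 0.690. Week 1: √(0.310/0.100) = 1.76. Week 8: √(0.310/0.570) = 0.74.

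**Ratio for change from baseline, equal variances:**

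| True correlation | Structure | Wk 1 | Wk 2 | Wk 4 | Wk 8 |
|---|---|---|---|---|---|
| 0.7 per week | Toeplitz | 1.25 | 1.18 | 1.06 | 1.00 |
| 0.8 per week | Toeplitz | 1.30 | 1.24 | 1.10 | 1.00 |
| 0.9 per week | Toeplitz | 1.35 | 1.32 | 1.15 | 1.00 |
| 0.7 per week | Compound symmetry | 1.48 | 1.13 | 0.93 | 0.83 |
| 0.9 per week | Compound symmetry | 1.76 | 1.28 | 0.95 | 0.74 |
| Constant 0.6 | Toeplitz or compound symmetry | 1.00 | 1.00 | 1.00 | 1.00 |

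AR(1) is close to Toeplitz under decay. Under constant correlation 0.6 it overstates the SE of change by 26–48% at Weeks 2–8.

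**Visit means, equal variances.** The ratio is 1.00 at all five visits for all three structures and every correlation pattern. With 16.7% dropout (40/240, reading the 200 evaluable patients as the rest) unrelated to outcome, it is 0.98–1.00 under Toeplitz.

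**SD falling from 1.2 to 0.9, Toeplitz, r = 0.7–0.9.** The result depends on the path:

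| Path of the SD | Mean, baseline | Mean, Wk 8 | Change, Wk 1 | Change, Wk 8 |
|---|---|---|---|---|
| Even by visit | 0.88 | 1.17–1.18 | 1.10–1.18 | 0.99–1.00 |
| Even by week | 0.90–0.91 | 1.20–1.21 | 1.13–1.22 | 1.03 |
| 1.2, 1.1, 1.0, 0.9, 0.9 | 0.86–0.87 | 1.15–1.16 | 1.07–1.14 | 0.97 |

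Hand check of the first row: the single fitted SD is close to the root mean square, √[(1.440 + 1.266 + 1.103 + 0.951 + 0.810)/5] = 1.055. Then 1.055/1.2 = 0.88 and 1.055/0.9 = 1.17.

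**Change as the outcome.** SAP 4.10.3 does not say whether change is a contrast between modelled visits or is itself modelled. In the second case, with r = 0.7–0.9 and equal raw variances, Toeplitz gives 1.45–1.76 at Week 1 and 0.82–0.74 at Week 8.

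**The case against.** The strongest reply is that nothing in the documents shows any SE to be wrong. This stands. A reader might infer from the mismatch with the schedule that the QOLRAD standard errors are wrong. That does not follow, because the true covariance is unknown, and under constant correlation with equal variances Toeplitz and compound symmetry are exact. Spacing alone also leaves the SEs of visit means right, so the exposure is mainly in change from baseline. The direction is not fixed either. With baseline modelled and equal variances, Toeplitz errs towards SEs that are too large. Understatement needs the compound-symmetry fallback, change as the modelled outcome, or unequal variances, and in the falling-SD examples even the sign at Week 8 depends on the path.

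A second reply is that little depends on this. That also stands. SAP 4.10.1.4 plans no formal testing, Protocol 9.4.7 treats the secondary endpoints descriptively, and Phase 3 dose selection rests on healing, safety and pharmacokinetics (Protocol 2.2). It would be wrong to infer that an error rate or the primary conclusion is affected.

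The reply does not remove the point. Change from baseline is the stated endpoint, and its SE is the quantity at risk. The equal-variance assumption can disturb the visit means too. The first fallback, compound symmetry, carries a risk of false precision at Week 8.

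**Conclusion.** The point holds as a possible bias, not as a demonstrated error. The named structures do not fit the QOLRAD schedule, and no robust SE protects against that. If correlation falls by a factor of 0.7–0.9 per week, variances are equal and baseline is a modelled visit, the Toeplitz SE of change is 25–35%, 18–32% and 6–15% too large at Weeks 1, 2 and 4, and about right at Week 8. Under compound symmetry it is 48–76% too large at Week 1 and 17–26% too small at Week 8. If the SD falls from 1.2 to 0.9, Toeplitz visit-mean SEs are about 9–14% too small at baseline and 15–21% too large at Week 8, depending on the path. All of these rest on assumed covariances. Severity is minor. The equally spaced weekly diary data do not share the spacing problem.

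**What to change.** For QOLRAD, fit an unstructured covariance: 5×6/2 = 15 parameters for five visits in about 240 patients, against 5 for Toeplitz. In large samples with complete data its SE ratio is 1.00 in every scenario tried. If it does not converge, use heterogeneous spatial power in actual weeks with sandwich SEs. State whether baseline is a modelled visit or change is the outcome. Keep Toeplitz for the diary.

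The SAP amendment was itself written after unblinding (its Section 3), and its Section 4.3.3 treats results not defined in the original SAP as formally exploratory. So the new fit should be reported as a labelled sensitivity analysis beside the prespecified model, not in place of it. The cost is one model option, a few lines of text and an extra set of QOLRAD outputs. No new data are needed.
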